11.1.4.3.1 Definition of Efficacy Endpoints

The exploratory efficacy endpoints assessed for 12 months of treatment are:

- Change in daily "ON" time without troublesome dyskinesia (defined as the sum of "ON" time without dyskinesia and "ON" time with non-troublesome dyskinesia) from Baseline to the 12-month visit based on home "ON/OFF" diaries.
- Change in daily "OFF" time from Baseline to the 12-month visit, based on home "ON/OFF" diaries.
- Change in total daily dose of oral LD/DDI from Baseline to the 12-month visit.
- Proportion of responders at the 12-month visit based on daily "OFF" time recorded in home "ON/OFF" diaries. A responder is defined as a subject that experiences ≥50% reduction in "OFF" time from Baseline.
- Change in daily "ON" time with troublesome dyskinesia in a subset of subjects who had more than 1 hour of troublesome dyskinesia at Baseline, based on home "ON/OFF" diaries from Baseline to the 12-month visit.

- Change in PDQ-39 scores from Baseline to the 12-month visit.
- Change in EQ-5D-5L scores from Baseline to the 12-month visit.
- Change in UPDRS Part II (ADL) from Baseline to the 12-month visit.
- Change in CGI-Severity and CGI-Improvement from Baseline to the 12-month visit.
- Change in SGI-Improvement from Baseline to the 12-month visit.
- Change in PDSS total score from Baseline to the 12-month visit
- Change in UPDRS Part III (motor score) from Baseline to the 12-month visit.
- Change from baseline to month 12 in percentage of "OFF" time and percentage of 'Good' ON during the first 3 hours since the subject is awake after 06:00 (6 am)
- Change from baseline to month 12 in ND0612 total dose
- Proportion of patients who reduced ND0612 total dose at any time during the study

The first efficacy endpoint of the change from Baseline to Month 12 in daily "ON" time without troublesome dyskinesia will be based on subject diary data. This will be a within group analysis for each treatment regimen. Subjects will provide data on daily "ON" and "OFF" time for the 2 days prior to the following visits: Baseline (Cohort 2 only), Months 1, 3, 6, 9, and 12 and the Early termination visit (if applicable) and additionally at Months 18, 24, 30, and 36 of the extension period. Subjects in Cohort 1, will be excluded from this analysis.

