with non-troublesome dyskinesia, “ON” without dyskinesia, Asleep. If there are duplicate entries (i.e., multiple entries recorded with same date and time interval), the worst entry will be used for the date and time interval in question. The worst entry will be selected in the order defined above.

- The diary day data expressed as hours will be normalized to 16 waking hours per day: The daily “ON” time without troublesome dyskinesia (“GOOD ON”) will be extrapolated to a 16 hour period by determining the proportions of “ON” time without troublesome dyskinesia among accurately recorded entries, excluding Asleep time and missing/non-valid recordings, and by multiplying this proportion by 16 hours. In addition, daily “ON” time without troublesome dyskinesia will be expressed as the percentage (%) of daily “ON” time without troublesome dyskinesia during waking hours (by multiplying the proportion by 100). However, only a single p-value applicable to both the percentage and number of hours will be reported.
- The mean daily “ON” time without troublesome dyskinesia (“GOOD ON”) prior to each visit will be calculated as mean value of the valid days documented in the patient’s diary prior to that visit. In case there are gaps within the 2 days preceding the visit, the last 2 recorded days before the visit will be used regardless of the gaps (as long as all days are within 7 days from the visit). If there are more than 2 valid days, only the last 2 days will be used. If there is only 1 valid day, the data from this day will be used.
- The Baseline for the home diary for subjects in Cohort 2 is defined as 2 consecutive days prior to the Baseline visit. The diaries collected at the subsequent visits after baseline will be used as response variables.

3.2.3.2. Change in daily “OFF” time based on home "ON/OFF" diaries from Baseline to the 12-month visit.

- The daily “OFF” time will be derived similarly as the daily “ON time without troublesome dyskinesia in 3.2.3.1.

3.2.3.3. Change in daily “ON” time without any dyskinesia (troublesome or non-troublesome) based on home "ON/OFF" diaries from Baseline to the 12-month visit.

- The daily “ON” time without any dyskinesia will be derived similarly as the daily “ON time without troublesome dyskinesia time in 3.2.3.1.

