- 3.2.3.4.** Change from baseline to month 12 in percentage of “OFF” time during the first 3 hours since the subject is awake after 06:00 (6 am), based on subject’s “ON/OFF” diary assessments on the 3 consecutive days before the visit.
- Subject will be declared as ‘awake’ if found not ‘asleep’ for at least 2 hours after 06:00 (6 am)
 - This endpoint will be derived similarly as the daily “ON time without troublesome dyskinesia in 3.2.3.1. However, only data recorded after 06:00 (6 am) will be used for derivation. At least 5 out of 6 half-hour periods (3 hours) are required to be completed, in order to classify a diary day as valid.
- 3.2.3.5.** Change in total ND0612 total dose from baseline to month 12
- 3.2.3.6.** Proportions of patients who reduced their total ND0612 total dose during 12 month of treatment
- 3.2.3.7.** Proportion of responders at the 12-month visit based on daily “OFF” time recorded in "ON/OFF" diaries. A responder is defined as a subject that experiences $\geq 50\%$ reduction in “OFF” time from Baseline.
- The daily “OFF” time will be calculated as defined in 3.2.3.2. The percentage reduction will be calculated as $(OFF_{\text{Month 12}} - OFF_{\text{baseline}}) / OFF_{\text{baseline}} * 100$. The subjects will be dichotomized as having a percentage reduction of $\geq 50\%$ versus a reduction of $< 50\%$. The patients with missing “OFF” time will be imputed with last available ‘OFF’ time value. .
- 3.2.3.8.** Change in daily “ON” time with troublesome dyskinesia in a subset of subjects who had more than 1 hour of troublesome dyskinesia at Baseline based on home "ON/OFF" diaries from Baseline to the 12-month visit.
- The daily “ON” time with troublesome dyskinesia will be derived similarly as the daily “ON time without troublesome dyskinesia in 3.2.3.1.
- 3.2.3.9.** Change in PDQ-39 summary index and the 8 dimension scores from Baseline to the 12 month visit
- The PDQ-39 questionnaire provides scores on eight dimensions as outlined below:

- mobility (10 items, #1 to 10)
- activities of daily living (6 items, #11 to 16)
- emotional well-being (6 items, #17 to 22)
- stigma (4 items, #23 to 26)
- social support (3 items, #27 to 29)
- cognitions (4 items, #30 to 33)
- communication (3 items, #34 to 36)
- bodily discomfort (3 items, #37 to 39).

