8.2. Exploratory Efficacy Variable(s) and Analysis

8.2.1. Change in daily “ON” time without troublesome dyskinesia (“GOOD ON”) from Baseline to each visit

The changes from baseline to all post-baseline visits within each treatment regimen and the difference between the 2 treatment regimens in “GOOD ON” time (defined as the sum of "ON" time without dyskinesia and “ON” time with non-troublesome dyskinesia) will be estimated using a Mixed Model for Repeated Measures (MMRM). The model includes response data from all post-baseline visits with no imputation for missing data. The “GOOD ON” time at baseline will be included as a covariate and the treatment regimen (Regimen 1 or Regimen 3), visit (Month 1, 3, 6, 9 or 12) and the interaction between treatment regimen and visit will be included as fixed factors in the model. An unstructured covariance structure will be assumed and the denominator degrees of freedom will be computed using the Kenward-Roger method. In case the model will not converge

with the unstructured covariance structure, the heterogeneous compound symmetry (CSH) and the heterogeneous Toeplitz structure (TOEPH) will be used instead (in that order). Both the changes from baseline within each treatment regimen and the difference between the regimens will be estimated, separately for each visit, from the same MMRM using contrasts. Since ON/OFF diaries were assessed differently for Cohort 1, this cohort will be excluded from the model.

The changes in “GOOD ON” time will be estimated both as hours (normalized to 16 hours of awake time) and as a percentage out of awake time during the 24 hours of data collection. However, only one p-value will be provided due to the fact that the p-values will be identical.

The SAS code planned for the analysis is outlined below.

```
PROC MIXED DATA=DATA;  
CLASS TRTP AVISIT USUBJID;  
MODEL CHG=BASE TRTP AVISIT TRTP*AVISIT / SOLUTION DDFM=KR;  
REPEATED AVISIT / SUBJECT=USUBJID TYPE=UN;  
LSMEANS TRTP*AVISIT / PDIFF CL;  
WHERE AVISIT IN ('MONTH 1', 'MONTH 3', 'MONTH 6', 'MONTH 9', 'MONTH 12' ) AND COHORT=2;  
RUN;
```

8.2.2. Change in daily “OFF” time based on home "ON/OFF" diaries from Baseline to the 12-month visit

The daily “OFF” time will be analyzed similarly as the “GOOD ON” time replacing baseline “GOOD ON” time with baseline “OFF” time as covariate.

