8.2.3. Change in daily “ON” time without any dyskinesia (troublesome or non-troublesome) based on home "ON/OFF" diaries from Baseline to the 12-month visit.

The daily “ON” time without any dyskinesia will be analyzed similarly as the “GOOD ON” time replacing baseline “GOOD ON” time with baseline “ON” time without any dyskinesia as covariate.

8.2.4. Proportion of responders at the 12-month visit based on daily “OFF” time recorded in home "ON/OFF" diaries. A responder is defined as a subject that experiences $\geq 50\%$ reduction in “OFF” time from Baseline.

The proportion of patients fulfilling the response criterion will be tabulated by visit. In addition, cumulative percentage of patients with reduction in “OFF” time normalized to a 16-hour waking day will be plotted as a function of percent reduction in “OFF” time from baseline to Month 12..

8.2.5. Change in daily “ON” time with troublesome dyskinesia in a subset of subjects who had more than 1 hour of troublesome dyskinesia at Baseline based on home “ON/OFF” diaries from Baseline to the 12-month visit.

The daily “ON” time with troublesome dyskinesia in the subset of subjects who had more than 1 hour of troublesome dyskinesia at Baseline will be analyzed similarly as the “GOOD ON” time replacing baseline “GOOD ON” time with baseline “ON” time with troublesome dyskinesia as covariate.

8.2.6. Change in PDQ-39 summary index and the 8 dimension scores from Baseline to the 12-month visit

The PDQ-39 summary index and the 8 dimension scores will be analyzed similarly as the “GOOD ON” time replacing baseline “GOOD ON” time with baseline PDQ-39 as covariate.

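### Troublesome-dyskinesia change is estimated only in subjects selected for a high baseline value of the same diary variable, so the within-regimen result includes regression to the mean

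*SAP*

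**What the plan says.** SAP 3.2.3.8 defines the endpoint as the change in ON-state "time with troublesome dyskinesia in a subset of subjects who had more than 1 hour of troublesome dyskinesia at Baseline based on home" diary entries. Protocol 11.1.4.3.1 lists the same endpoint, with change assessed "in a subset of subjects who had more than 1 hour of troublesome dyskinesia at Baseline, based on home" diary entries. SAP 8.2.5 states that this outcome "in the subset of subjects who had more than 1 hour of troublesome dyskinesia at Baseline will be analyzed similarly" to GOOD ON time, with baseline troublesome-dyskinesia time as the covariate.

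The baseline comes from SAP 3.2.3.1, whose derivation this endpoint follows: "The Baseline for the home diary for subjects in Cohort 2 is defined as 2 consecutive days prior to the Baseline visit". Incomplete diaries are allowed: "If there is only 1 valid day, the data from this day will be used". No separate diary is set aside for selection.

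The model in SAP 8.2.1 is "MODEL CHG=BASE TRTP AVISIT TRTP*AVISIT / SOLUTION DDFM=KR", restricted to Cohort 2. It gives the change from baseline within each regimen at each visit and the difference between regimens. Both regimens are open-label ND0612.

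The objectives (Protocol 7.3, SAP 2.3) carry the same restriction to subjects above 1 h. The only summary of troublesome-dyskinesia hours not limited to that subset is at baseline (SAP 6.3).

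**The concern.** One noisy measurement does two jobs: it decides who enters the analysis, and it is the reference from which change is measured. Subjects recorded on unusually bad days are selected in, and those recorded on unusually good days are left out. At follow-up the subset mean is expected to fall towards each subject's usual level, whatever the drug does.

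The within-regimen change has nothing to offset this, because no group goes without ND0612. A null effect, or a modest worsening, could be read as a reduction in troublesome dyskinesia. SAP 5.3 plans nominal two-sided 0.05 tests and SAP 8.2.1 requests confidence limits, so the estimate may be reported with apparent statistical support.

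The matching upward drift falls in subjects at or below 1 h. They are also the ones who could newly develop more than 1 h of troublesome dyskinesia, and their post-baseline hours are not reported.

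**Working it through.** **No figure to reproduce.** The documents give no SD, correlation, subset size or power for this endpoint, and no formal sample-size calculation was made (Protocol 11.2, SAP 3.3). From the documents come the 1 h cut-off, the one- or two-day baseline, the model and the absence of an untreated control. All distributions and correlations below are assumptions. Every result assumes no drug effect unless stated.

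**Step 1: normal theory.** Let baseline and follow-up have mean m, standard deviation SD and correlation ρ, with cut-off c = 1 h and a = (c − m)/SD. Then

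E[change | baseline > c] = −(1 − ρ) × SD × φ(a) / (1 − Φ(a)).

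Example with m = 1.0, SD = 1.5, ρ = 0.7: a = 0, φ(0) = 0.399, 1 − Φ(0) = 0.5, ratio 0.798. Change = −0.3 × 1.5 × 0.798 = −0.36 h. The unselected half changes by +0.36 h, so all subjects together change by 0.

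**Step 2: skewed models.** Many subjects will have no troublesome dyskinesia, so two simulations were run.

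- *Gamma diary days:* 50–70% of subjects with almost no troublesome dyskinesia, the rest exponential with mean 1.5–2.5 h, day-to-day CV 0.5–1.2, two-day means at both times. This selects 12–32% of subjects.
- *Zero-inflated log-normal:* 50% or 65% zeros, median 1.2 h if non-zero, log-SD 0.9, rounded to 0.25 h. This selects 18–26%, with a subset baseline mean of about 2.8 h.

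| Model | Correlation of baseline and follow-up diary values | Change in >1 h subset (h) |
|---|---|---|
| Normal (m 0.5–1.5, SD 1.0–2.0) | 0.9 | −0.11 to −0.13 |
| Normal | 0.7 | −0.34 to −0.39 |
| Normal | 0.5 | −0.57 to −0.65 |
| Gamma | about 0.86 | −0.06 to −0.10 |
| Gamma | about 0.73 | −0.22 to −0.30 |
| Gamma | about 0.57 | −0.62 to −0.72 |
| Log-normal | 0.84–0.85 | −0.22 to −0.29 |
| Log-normal | 0.58–0.60 | −0.64 to −0.81 |
| Log-normal | 0.36–0.39 | −1.05 to −1.28 |
| Log-normal | 0.19–0.21 | −1.42 to −1.70 |

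Subjects at or below 1 h drift up by 0.02 to 0.23 h in the gamma model and by 0.07 to 0.51 h in the log-normal model. In the gamma model 2–10% of them exceed 1 h at follow-up by chance. The all-subject mean change is 0.00 to 0.01 h.

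**Step 3: does the baseline covariate help?** Least-squares means are evaluated at the mean of the covariate in the data analysed, here the selected subset. A fitted line passes through the point of means, so for one group with complete data the adjusted mean change equals the raw one. The log-normal simulation shows this in every zero-effect scenario (for example −0.64 h both ways). With two regimens the covariate mean is pooled. That can move the regimens slightly relative to each other but leaves the common bias.

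**Step 4: chance of a nominally significant reduction** (log-normal model, one-sample t-test, two-sided 0.05). Without bias it would be 0.025 in this direction. The subset sizes are illustrative.

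| Latent correlation (observed) | n = 20 | n = 40 |
|---|---|---|
| 0.9 (0.84–0.85) | 0.12–0.16 | 0.17–0.24 |
| 0.7 (0.58–0.60) | 0.28–0.38 | 0.44–0.57 |
| 0.5 (0.36–0.39) | 0.46–0.60 | 0.70–0.83 |

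**Step 5: true worsening of 0.3 h in everyone** (log-normal model). The subset still shows −0.14 to −1.42 h at latent correlations 0.3–0.8, and 0.00 to +0.08 h at 0.9. The all-subject mean change is +0.27 to +0.28 h, slightly under 0.3 because of rounding.

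**The case against.** The strongest reply is that the SAP does what the protocol asks. Every statement of the objective is limited to subjects above 1 h at baseline, the subset is prespecified, the endpoint is exploratory, and SAP 8.1 disclaims formal testing. This stands. A reader might infer that the SAP has narrowed an all-subject objective; the documents show it has not. Prespecification does not remove the bias, however, and where the aim is estimation a biased estimate still matters.

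A reader might also infer that worsening in everyone else goes unexamined. That is too strong:

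- GOOD ON and OFF are analysed in all Cohort 2 mITT subjects. Waking time is normalised to 16 h, so OFF + GOOD ON + troublesome ON = 16. For observed means in the same subjects, the all-subject change in troublesome ON is minus the sum of the other two changes.
- SAP 4.5 and 8.3 split GOOD ON by baseline troublesome dyskinesia at 1 h.
- SAP 7.3.4 requires a time-to-first-onset analysis of dyskinesia TEAEs in the Safety Set.

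None of these gives troublesome-dyskinesia hours after baseline in subjects at or below 1 h, or counts those who newly exceed 1 h. Adverse-event reports are not diary hours, and Protocol 10.1.1 exempts anticipated fluctuations that are not clinically significant.

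Nor is every estimate affected alike. Both regimens pass the same cut-off, so most of the bias cancels in their difference. Cancellation is approximate, because Regimen 3 was allocated after a protocol amendment and not randomised against Regimen 1.

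Finally, the size is driven by assumptions. At the low end it is 4 to 6 minutes (0.06–0.10 h), well under one 30-minute diary interval. That is correct, and no single figure should be attached to this point.

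**Conclusion.** The concern holds for the within-regimen change in the above-1 h subset. Its direction follows from the definition: a reduction is expected whenever repeat diary values correlate below 1, and the planned covariate does not remove it. Its size cannot be fixed from the documents. It runs from under 0.1 h with very stable diaries to over 1 h with low correlation, under the assumed distributions.

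The regimen difference is much less affected, and the primary safety analysis is not touched. It does not follow that a reported reduction would be false, only that the subset change alone cannot separate a drug effect from selection. The gap in coverage is narrow: no direct report of troublesome-dyskinesia hours, or of new crossings of 1 h, among subjects at or below 1 h at baseline.

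**What to change.** Keep the prespecified subset analysis in SAP 3.2.3.8 and 8.2.5. Add a statement that its within-regimen change includes regression to the mean and is not by itself evidence of a drug effect. Beside it, report:

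1. The same MMRM for troublesome-dyskinesia time in all Cohort 2 mITT subjects with diary data, with baseline as covariate. This removes the selection on baseline, though it remains an uncontrolled before-and-after change.
2. A shift table by visit and regimen, ≤1 h versus >1 h at baseline and at the visit, showing both directions. Some crossing is expected by chance (2–10% upward in the gamma model), so neither direction should be read alone.

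List both additions in SAP section 10. Replacing the subset as the main analysis would depart from the protocol objective and is not needed. Selecting a dyskinetic group on the Day 1 UPDRS Part IVA score is optional only: it defines a different population and is rated just after the baseline diary days, so some shared fluctuation may remain.

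The cost is one extra model and one table on data already collected, and a less favourable reading of the subset result.

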10.2.1.5 Quality of Life in Parkinson's Disease (PDQ-39)

Their perception of QoL will be rated by the subjects on Day 1, Week 1, Months 1, 3, 6, 9, 12 and the Early termination visit (if applicable) using the PDQ-39 ([21] see

Appendix 17.7) a 39-item questionnaire with 8 discrete scales: mobility (10 items), ADL (6 items), emotional well-being (6 items), stigma (4 items), social support (3 items), cognitions (4 items), communication (3 items), and bodily discomfort (3 items).

Subjects are asked to think about their health and general well-being and to consider how often in the last month they have experienced certain events (e.g., difficulty walking 100 yards). Subjects are asked to indicate the frequency of each event by selecting 1 of 5 options (Likert Scale): never/occasionally/sometimes/often/always or cannot do at all.

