Items are scored from 0 (never) to 4 (always). Dimension scores are obtained by dividing the sum of the item scores by the maximum possible score for any given dimension and expressing this as a percentage. For example:

- mobility = (sum of scores of #1 to 10)/(4 x 10) x 100
- activities of daily living = (sum of scores of #11 to 16)/(4 x 6) x 100.

For social support, if the response indicates that a patient does not have a spouse or partner for #28, social support can be calculated as [(sum of scores of #27 and 29)/(4 x 2) x 100].

A summary index is then calculated as the sum of the total score of the dimensions divided by the number of dimensions, i.e. (sum of dimension scores / 8). If any item score is missing, the relevant dimension score and the summary index will be missing.

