3.2.3.13. Change in SGI-Improvement from Baseline to the 12 month visit.

- This variable will be derived in a similar way as CGI-I described in 3.2.3.12.

3.2.3.14. Change in PDSS total score from Baseline to the 12 month visit.

- Each of the 15 items is scored on a 5-point scale (from 0 indicating no symptoms to 4 indicating maximum symptoms). The total score is calculated as a sum score of the 15 items. In case a single item is missing, the total score will be set as missing.

3.2.3.15. Change in UPDRS Part III (motor score) from Baseline to the 12 month visit.

- The UPDRS part III (motor) score will be calculated as the sum of the individual items 18-31. UPDRS scores will be gathered during visit but not at pre-specified time points. Missing individual items will not be imputed. If there is at least 1 missing item, the corresponding sum score will be set as missing.

3.2.3.16. Change in ND0612 Dose - Data on ND0612 dose reduction will be assessed as change from baseline in total daily of LD dose.

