7.5. Secondary Safety Analyses

C-SSRS: The C-SSRS is a measure of suicidal ideation and behavior. The rating scale has 4 general categories: suicidal ideation, intensity of ideation, suicidal behavior, and actual attempts. All C-SSRS data will be listed. The frequency and percentage of patients with each response for suicidal ideation, intensity of ideation, and suicidal behavior items will be summarized as appropriate by visit.

QUIP: The QUIP is an instrument used to measure the extent of impulsive and compulsive behaviors in PD patients. The QUIP has 3 sections: Section 1 assesses any impulsive control disorder (gambling, sexual, buying, and eating disorders); Section 2 assesses other compulsive behaviors (punding, hobbyism, and walkabout); and Section 3 assesses compulsive medication use. All QUIP scores (A: gambling, B: sex, C: buying, D: eating, total ICD score (A-D), E: hobbyism-punding, F: PD medication use and total QUIP score (A-F)) will be summarized with descriptive statistics by visit. In addition, the changes from baseline will be summarized.

ESS: The ESS is used to determine the level of daytime sleepiness. There are 8 situations listed for which patients rate their likelihood of dozing or sleeping (0=would never doze or sleep, 1=slight chance of dozing or sleeping, 2=moderate chance of dozing or sleeping, and 3=high chance of dozing or sleeping). The total score is the sum of 8 item scores and can range between 0 and 24. If any item score is missing, the total score will be missing. The higher total score indicates the higher level of daytime sleepiness. A score of 10 or more is considered sleepy, and a score of 18 or more is very sleepy. The ESS score will be summarized with descriptive statistics by visit. In addition,

the proportion of patients who are sleepy (score of 10 or more) or very sleepy (score of 18 or more) will be tabulated by visit and treatment group.

The influence of the pump system malfunctions on the safety of ND0612 will be evaluated by capturing data on the date and time of malfunctions, including the description of the malfunction, association to an AE and the action taken. All data collected for the pump system malfunctions will be listed. In addition, the following will be tabulated by treatment group:

- The number of pump system malfunctions and the number of subjects with at least one pump system malfunction

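### One blank item voids the PDQ-39 summary index and other multi-item scores, and a blank at baseline removes the subject from that score's model at every visit

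*SAP*

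**What the plan says.** The Protocol (10.2.1.5) describes the PDQ-39 as a "39-item questionnaire with 8 discrete scales". SAP 3.2.3.9 scores each dimension as a percentage of its maximum and averages the eight dimensions into a summary index. It then sets the rule "If any item score is missing, the relevant dimension score and the summary index will be missing". The one relief is for social support, which is scored from two items "if the response indicates that a patient does not have a spouse or partner for #28".

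The SAP repeats the rule for other scales:

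- UPDRS Part II (3.2.3.11, items 5-17) and Part III (3.2.3.15, items 18-31): "If there is at least 1 missing item, the corresponding sum score will be set as missing".
- PDSS (3.2.3.14, 15 items): "In case a single item is missing, the total score will be set as missing".
- ESS (7.5, 8 items): "If any item score is missing, the total score will be missing".

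SAP 8.2.6, 8.2.8, 8.2.11 and 8.2.12 analyse the PDQ-39 index and dimensions, UPDRS II, the PDSS and UPDRS III with the model of 8.2.1. Its response is change from baseline, its covariate is the baseline value, and it covers Months 1, 3, 6, 9 and 12. The ESS is handled differently: "The ESS score will be summarized with descriptive statistics by visit".

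SAP 5.4 plans no imputation unless specified. Neither document has a rule for scoring incomplete forms of these scales, or a sensitivity analysis for them.

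**The concern.** The chance that a form has at least one blank rises with the number of items, so a strict rule bears hardest on the longest score, the 39-item index. A subject who answered 38 items has no index at that visit.

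Baseline is the costlier place for a blank. The model can tolerate a missing follow-up visit, but a missing baseline leaves both response and covariate undefined on every row for that subject. SAP 5.2 would accept an earlier pre-dose value, but the Cohort 2 screening list (Protocol 9.1.1) contains no PDQ-39, PDSS or UPDRS, so none is scheduled. For Cohort 1 the baseline comes from study ND0612H-006, and the documents do not say whether an earlier value exists there.

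At stake is the precision of the quality-of-life, sleep and UPDRS estimates, and of the ESS summaries.

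**Working it through.** The plan has no figure to reproduce: there is no formal sample size evaluation (Protocol 11.2) and no item non-response rate.

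**Inputs from the documents.** PDQ-39 dimensions have 10+6+6+4+3+4+3+3 = 39 items. PDSS has 15, UPDRS II 13, UPDRS III 14 numbered items and ESS 8. The planned total is about 210 treated, of whom at most 36 are in Cohort 1, leaving 210 - 36 = 174 in Cohort 2 (illustration only; SAP 3.3 gives a smaller total, 120-170).

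**Assumptions.** The blank rate per item, p, is 0.1% to 2%. The intra-form correlation of blanks, ρ, is 0 to 0.30.

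**Strict rule.** With independent blanks, P(score void) = 1 - (1 - p)^k for k items. For the index at p = 1%: 1 - 0.99^39 = 0.324. With clustering (beta-binomial), P(void) = 1 - B(a, k + b)/B(a, b), where B is the beta function, a = p(1 - ρ)/ρ and b = (1 - p)(1 - ρ)/ρ.

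**Half-items rule.** A dimension of d items is scored if at most floor(d/2) are blank, and the index needs all eight dimensions. The probability was averaged over the same beta distribution.

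Share of forms with no PDQ-39 index:

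| p | Strict, ρ = 0 | Strict, ρ = 0.05-0.10 | Strict, ρ = 0.30 | Half-items, ρ = 0.05-0.10 | Half-items, ρ = 0.30 |
|---|---|---|---|---|---|
| 0.1% | 3.8% | 1.5-2.1% | 0.7% | 0.05-0.08% | 0.15% |
| 0.5% | 17.8% | 7.5-10.2% | 3.5% | 0.2-0.4% | 0.8% |
| 1% | 32.4% | 14.4-19.4% | 7.0% | 0.5-0.9% | 1.5% |
| 2% | 54.5% | 26.7-35.2% | 13.5% | 1.2-1.9% | 3.1% |

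With independent blanks the half-items rule loses at most 0.36% (p = 2%).

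**Shorter scores, independent blanks at p = 0.5% and 1%.** PDSS 7.2% and 14.0%; UPDRS II 6.3% and 12.3%; UPDRS III 6.8% and 13.1%; ESS 3.9% and 7.7%. Among PDQ-39 dimensions at p = 1%, a 10-item dimension loses 1 - 0.99^10 = 9.6% and a 3-item dimension 1 - 0.99^3 = 3.0%.

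**Baseline consequence.** Of 174 Cohort 2 subjects at p = 1%, the index model would lose 174 × 0.324 = 56 if blanks are independent, 25-34 at ρ = 0.05-0.10, and 12 at ρ = 0.30. In a simulated fit of change on baseline with 174 subjects and 5 visits, 33 subjects without a baseline lost all 33 × 5 = 165 of their rows, out of 174 × 5 = 870.

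**The case against.** The strict rule is prespecified, transparent and invents no values, in keeping with SAP 5.4. The loss may be small: at p = 0.1% it is 3.8% of index scores at most, and 0.7% with strong clustering. Questionnaires are completed around clinic visits, and Protocol 12.3 has missing data queried, which may reduce blanks. These points stand and limit the weight of the finding. They do not justify the rule, because queries cannot reliably recover a self-rated answer later, and item-level completeness review is specified only for the home diaries (Protocol 9.2.3).

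The half-items threshold has no source in either document. That is fair, and is a reason to keep both scorings. The social-support relief is not a precedent either: it covers an item that does not apply, not one left unanswered.

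Several stronger readings are tempting and are not supported:

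- *All other answers are discarded.* Only the affected dimension and the index are void. The other seven dimensions have their own models, and UPDRS Parts II and III are summed separately.
- *A subject needs complete forms at both baseline and Month 12.* The model uses five visits. A subject blank only at Month 12 stays in and still informs that estimate through the covariance.
- *The ESS loses subjects from a model.* It has no model.
- *Power falls by a calculable amount.* No power target exists, and SAP 8.1 plans no formal hypothesis testing.
- *The loss is known to be biased.* A link between blanks and disability is plausible but not documented. UPDRS III is a clinician's motor examination, so reasoning about self-completed forms does not carry over to it.
- *The rule shrinks the efficacy set.* SAP 4.4 defines mITT membership by the diary (Cohort 2) or UPDRS III data (Cohort 1), so PDQ-39, PDSS and ESS blanks do not affect it. Whether a single blank UPDRS III item would do so for Cohort 1 is not stated.

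**Conclusion.** The point holds as an avoidable loss of precision in exploratory scores (PDQ-39, PDSS, UPDRS II and III) and one secondary safety score (ESS). The mechanism follows directly from the SAP text. Its size does not: it rests on an assumed blank rate and an assumed degree of clustering, and for the index runs from 0.7% to 54.5% of forms across the range shown. In every clustered scenario the strict rule loses more than the half-items rule, about 4-5 times as much at correlation 0.30 and at least 13 times as much at 0.05-0.10. The primary analyses of adverse events, pain VAS and tolerability are unaffected. The change is worth making because it is cheap, not because the trial's main conclusion depends on it.

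**What to change.** Before database lock:

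1. Amend SAP 3.2.3.9 so that each PDQ-39 dimension is computed from its answered items, rescaled to 0-100, when at least half are answered. Compute the index when all eight dimensions are available. Keep the existing provision for item 28.
2. Apply the same at-least-half proration to the PDSS total (3.2.3.14) and the ESS total (7.5).
3. Leave UPDRS II and III as complete-item scores unless a numeric limit on missing items is stated and justified.
4. Keep complete-item scoring as a sensitivity analysis for every score that changes.
5. Report missing-item counts by scale and visit, with the number of subjects lacking a baseline score.

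The cost is SAP wording and a change to the derivation programs. No new data are needed, and Protocol 11.1.4.2 and 11.1.4.3.2 already leave these endpoint definitions to the SAP. The downside is that proration assumes the answered items represent the blank one; the sensitivity analysis shows how much that matters. If blanks prove rare, results will barely move.
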